8. RISKS

a. Medical risks, listing all procedures, their major and minor risks and expected frequency

NRT Gum or Lozenge

Although adverse effects from NRT gum or lozenge are uncommon. These may include:

- a) Nausea
- b) Abnormal dreams (vivid, unusual, strange)
- c) Constipation
- d) Flatulence
- e) Vomiting
- f) Rash
- g) Hypersensitivity reactions
- h) Sleep walking
- i) Accidental injury
- j) Interaction with alcohol
- k) Seizures
- l) Changes in mood
- m) Hallucinations
- n) Paranoia
- o) Delusions
- p) Homicidal ideation
- q) Aggression
- r) Hostility
- s) Agitation
- t) Anxiety
- u) Panic
- v) Suicidal Ideation
- w) mouth ulcers
- x) jaw muscle aches
- y) dizziness
- z) hiccups
- aa) headache
- bb) gastrointestinal symptoms (nausea, vomiting, diarrhea, dyspepsia)
- cc) dyspnea or difficulty breathing
- dd) abnormal heart beat (tachycardia, arrhythmias or palpitations)
- ee) rash

NRT Patch

Reported adverse effects include the following:

- a) Skin irritation
- b) dizziness,
- c) gastrointestinal symptoms (nausea, vomiting, diarrhea, dyspepsia)
- d) headaches
- e) rash
- f) abnormal heart beat (tachycardia, arrhythmias or palpitations)
- g) dyspnea or difficulty breathing

Chantix

Adverse reactions

- Most common adverse reactions (>5% and twice the rate seen in placebo-treated patients) were nausea, abnormal (e.g., vivid, unusual, or strange) dreams, constipation, flatulence, and vomiting.

Warnings & precautions

- Neuropsychiatric Adverse Events: Postmarketing reports of serious or clinically significant neuropsychiatric adverse events have included changes in mood (including depression and mania), psychosis, hallucinations, paranoia, delusions, homicidal ideation, aggression, hostility, agitation, anxiety, and panic, as well as suicidal ideation, suicide attempt, and completed suicide. They will be advised to seek immediate medical attention if they experience signs and symptoms of neuropsychiatric events.
- Seizures: New or worsening seizures have been observed in patients taking CHANTIX. CHANTIX should be used cautiously in patients with a history of seizures or other factors that can lower the seizure threshold. They will be advised to seek immediate medical attention if they experience signs and symptoms of seizure activity.
- Interaction with Alcohol: Increased effects of alcohol have been reported. We will instruct patients to reduce the amount of alcohol they consume until they know whether CHANTIX affects them.
- Accidental Injury: Accidental injuries (e.g., traffic accidents) have been reported. We will instruct patients to use caution driving or operating machinery until they know how CHANTIX may affect them.
- Cardiovascular Events: Patients with underlying cardiovascular (CV) disease may be at increased risk of CV events; however, these concerns must be balanced with the health benefits of smoking cessation. We will instruct patients to notify our team *and* their healthcare provider of new or worsening CV symptoms. They will be advised to seek immediate medical attention if they experience signs and symptoms of myocardial infarction (MI) or stroke.
- Somnambulism: Cases of somnambulism have been reported in patients taking CHANTIX. Some cases described harmful behavior to self, others,

Date: 01/10/2024

Principal Investigator: [name]

Application Number: IRB00224186

or property. We will instruct patients to discontinue CHANTIX and notify their healthcare provider if they experience somnambulism.

- **Angioedema and Hypersensitivity Reactions:** Such reactions, including angioedema, infrequently life-threatening, have been reported. We will instruct patients to discontinue CHANTIX and immediately seek medical care if symptoms occur.
- **Serious Skin Reactions:** Rare, potentially life-threatening skin reactions have been reported. We will instruct patients to discontinue CHANTIX and contact a healthcare provider immediately at first appearance of skin rash with mucosal lesions.
- **Nausea:** Nausea is the most common adverse reaction (up to 30% incidence rate). Dose reduction may be helpful.

b. Steps taken to minimize the risks

- **Reporting of Adverse Events, Adverse Device Effects and Unanticipated Problems**

Definition of medication adverse event: An adverse event (AE) is any symptom, sign, or experience that develops during the course of administering NRT (gum, lozenges or patches) or non-nicotine pharmacotherapies (Chantix®)

The following report will be supplied as a narrative for all NRT-reported adverse events:

- Study identifier
- A description of the event
- Date of onset
- Current status
- Whether study medication was discontinued
- Whether alternative NRT or non-nicotine pharmacotherapy was prescribed
- Investigator assessment of the association between the event and study intervention

Patients will undergo a multistep process to screen and monitor adverse effects on therapy. The medications prescribed & delivered based on initial screening will only be recommended for administration after participants undergo confirmation of appropriateness of drugs selection at the time of the baseline study visit (WEEK 3). Participants will be provided a 24-hour contact phone number to report concerns or adverse effects on therapy. All concerns will be reviewed by the PI within 24 hours of receipt.

All adverse events will be followed until resolution, stabilization, or until it has been determined that the study intervention or participation is not the cause. Further action and/or candidacy for an alternative pharmacotherapy (e.g. Chantix® changed to NRT patch) will occur under the direction of the medical specialists (PI).

Date: 01/10/2024

Principal Investigator: [name]

Application Number: IRB00224186

We will also ensure that Chantix is being administered to the correct participants and drug education is being delivered at each study visit through the completion of medication dispensing form (**see “Supplementary Document 5”**). The form requires the signature of the study team member who will verify administration and education of the medication to the correct participant.

c. Plan for reporting unanticipated problems or study deviations

All unanticipated problems and study deviations will be reviewed by the PI [name].

We have built the protocol to accommodate minor deviations. For example, our protocol is still maintained despite participants unable to attend the study visits or if all outcomes are not obtained during the 4 week trial. These will be reported in an IRB continuing review.

Major deviations will be reported immediately to the IRB. A major deviations are events that cause or could cause harm to subjects or others or that affect the fidelity of our research.

d. Legal risks such as the risks that would be associated with breach of confidentiality

Not applicable

e. Financial risks to the participants

There are no financial risks for participants

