***NOTE 2:** Our 1st pilot at Douglass Homes did not result in any participant being excluded for being pregnant or breastfeeding. We do not anticipate more than 2 participants being excluded based on pregnancy or breastfeeding status. All women excluded for these criteria will be provided local smoking cessation resources in case they again start to smoke ([name] or Tobacco Treatment Clinic at Bayview Medical Center)

***NOTE 3:** Proof of insurance will be requested in the form of either the actual insurance card or image of the front and back of their insurance card. The pictures of the health insurance card will be uploaded in CRMS. The information will be used for pharmacotherapy billing

***NOTE 4:** Although we will not enroll those without active health insurance, we will provide contact information for the Maryland Health Connection (<https://www.marylandhealthconnection.gov/>). The Maryland Health Connection (administered by the Maryland Health Benefit Exchange) is the health insurance marketplace for the state.

If they meet *all* screening criteria, they will then undergo a pharmacologic screening questionnaire (**see “Supplementary Document 2”**) to determine what type of tobacco treatment “controller” medication would be appropriate (NRT transdermal patch or Varenicline (Chantix®)). This screening questionnaire is used in the Tobacco Treatment Clinic at Bayview Medical Center (Medical Director: [name]) for similar purposes. We are undertaking this step at this time point to ensure timely prescription and delivery of NRT products and/or Chantix®, if needed, prior to the start of the intervention.

Date: 01/10/2024

Principal Investigator: [name]

Application Number: IRB00224186

***NOTE 1:** All participants will receive an as-needed medication to address “acute” nicotine urges (NRT gum or lozenge) and a “controller” medication to address the overall nicotine addiction (NRT transdermal or Chantix®)

***NOTE 3:** Participants will be notified of their chosen “acute” and “controller” medication during the 4-week intervention. They will be provided a drug information handout that contains details of the drug, including common and rare adverse effects seen with the therapy [see “Supplementary Document 4”). Contraindications to therapy will also be verbally reviewed with the participant and a focus on the following 4 categories.

Absolute contraindications of NRT products:

NRT gum: Dysphagia and subsequent aspiration risk

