 - Participants will complete baseline surveys that capture sociodemographic and smoking characteristics (see “Supplementary Document 3”). Participants will be allowed sufficient time (no limit) to complete the survey. For participants with difficulty reading the survey, the questions will be read aloud and the responses will be recorded. We anticipate that the survey will take no more than 5-10 minutes to complete since we purposely are acquiring fewer but impactful questions to minimize participant study burden.
- RE-confirmation of any potential contraindications for the prescribed NRT and non-nicotine pharmacotherapies – as chosen during screening. This review of contraindications will occur by our research team.

This step will duplicate the review of absolute and relative contraindications undertaken during the screening process:

- Absolute contraindications of NRT products
 - *NRT gum: Dysphagia and subsequent aspiration risk*
 - *NRT lozenge: Dysphagia and subsequent aspiration risk*
 - *NRT transdermal patch: Severe diffuse skin disease*
 - *Women who are pregnant or breastfeeding.*
- Relative contraindication of non-NRT products:
 - *Recent myocardial infarction (≤ 2 weeks), arrhythmias, angina, ulcers, uncontrolled high blood pressure, overactive thyroid, pheochromocytoma, or a dental condition or disorder.*
- Absolute contraindication of Chantix®:
 - *Inability to swallow pills*
 - *History of serious hypersensitivity or skin reactions to Chantix®*
 - *Women who are pregnant or breastfeeding*

- Relative contraindication of Chantix®:
 - Severe renal impairment (dosage adjustment is necessary)
 - Underlying neuropsychiatric disease
- ***NOTE:** If contraindications are noted, the team will immediately review them with the study's advanced practice provider (physician and/or pharmacist). If contraindications exist and the medical specialists determine the patient is not a suitable candidate any longer for the prescribed pharmacotherapies, the patient will be disenrolled from the study; they will be provided contact information of local smoking cessation resources ([name] and Tobacco Treatment Clinic at Bayview Medical Center). Modifications in acute and controller therapy dosing may be employed in conversations with our team's medical specialists (e.g., transdermal NRT patch in replacement of Chantix®).

2ND STEP – DRUG EDUCATION AND SIDE-EFFECT MONITORING

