6. DRUGS/ SUBSTANCES/ DEVICES

- **The rationale for choosing the drug and dose or for choosing the device to be used.**

Nicotine and non-nicotine pharmacotherapy to treat tobacco addiction will be prescribed in Epic by [name] [PI], Medical Director of the Tobacco Treatment Clinic at Bayview Medical Center. [name] is a faculty member in the Division of Pulmonary Critical Care & Medicine.

Pharmacotherapy oversight will also be led the PI, an expert in pharmacotherapy for tobacco dependence and smoking cessation.

The selection and prescription of pharmacotherapies will approximate an approach currently employed the PI. The PI currently provides medical care in two public housing complexes in Baltimore: Monument East and McColloch Homes.

Patients will undergo a multistep process to screen and monitor adverse effects on therapy. The medications chosen based on initial screening will be prescribed and delivered to participants. Prior to initiating the administration of the medications, participants will again be evaluated for the presence of absolute or relative contraindications of the prescribed pharmacotherapy regimen (BASELINE VISIT: Time Point 3). Participants will be provided a 24-hour contact phone number to report concerns or adverse effects on therapy. All concerns will be reviewed by the PI within 24 hours of receipt.

All pharmacotherapy is FDA approved and dosing will be based on FDA drug labelling.

- NRT gum or lozenge:

Baseline to end of study = 4 weeks	
STEP 1	Determine dosage
Do you smoke your 1 st cigarette within 30 minutes of waking up?	
Yes → Use 4 mg gum or lozenge	
No → Use 2 mg gum or lozenge	
STEP 2	Frequency of administration
Take the recommended dose (1-piece) by mouth every 1-2 hours	

- NRT patch:

Baseline to end of study = 4 weeks	
STEP 1	Determine dosage

Date: 01/10/2024

Principal Investigator: [name]

Application Number: IRB00224186

Do you smoke \geq 10 cigarettes per day? Yes \rightarrow Use 21 mg patch No \rightarrow Use 14 mg patch
STEP 2 Frequency of administration
Apply one new patch per day

- Chantix®:

Baseline to end of study = 4 weeks
STEP 1 Dosing & administration
Day 1 – 3: 0.5 mg by mouth daily Day 4 – 7: 0.5 mg by mouth twice-daily Day 8 – 30: 1 mg by mouth twice-daily

- Justification and safety information if FDA approved drugs will be administered for non-FDA approved indications or if doses or routes of administration or participant populations are changed.

Not applicable

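### The protocol tells prescribers to use Chantix with caution after seizures, but neither the screening list nor the baseline re-check list prompts staff to ask about them.

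*Combined protocol and SAP*

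**What the plan says.** The Chantix warnings in Section 8a (Medical risks) include one on seizures: "CHANTIX should be used cautiously in patients with a history of seizures or other factors that can lower the seizure threshold". The only action stated there is that participants be told to get urgent care if seizure signs develop.

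Section 4 describes two reviews of contraindications before treatment starts.

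- **Screening (Time Point 1).** The protocol says: "Contraindications to therapy will also be verbally reviewed with the participant and a focus on the following 4 categories". The four categories are then listed.
- **Baseline (Time Point 3, Part 2, 1st step).** Staff carry out "RE-confirmation of any potential contraindications for the prescribed NRT and non-nicotine pharmacotherapies". On content, the text says: "This step will duplicate the review of absolute and relative contraindications undertaken during the screening process". On who does it: "This review of contraindications will occur by our research team". The same four categories are printed again. A note gives the route for a positive answer: "If contraindications are noted, the team will immediately review them with" the study's advanced practice provider.

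Two other sections make the baseline review a check before dosing. Section 6 says that, before medication is started, "participants will again be evaluated for the presence of absolute or relative contraindications of the prescribed pharmacotherapy regimen". Section 8b says the delivered medications "will only be recommended for administration after participants undergo confirmation of appropriateness of drugs selection at the time of the baseline study visit".

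At both steps the printed relative contraindications of Chantix are severe renal impairment and underlying neuropsychiatric disease.

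**The concern.** A caution that depends on a patient's history works only if someone asks about that history before the first dose. The protocol states the caution in its risk section but does not carry it into either list that staff use to ask the questions. Because the baseline review is written as a repeat of the screening review, it inherits the omission and offers no printed safeguard if screening missed the history.

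What is at stake is patient safety. A participant with past seizures could start Chantix without a clinician having weighed the caution. At baseline, discovery would depend on staff going beyond the list or on the participant volunteering the information.

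**Working it through.** No statistical calculation applies. The check sets the Section 8a warning beside every printed list that could prompt for it and counts the items.

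| Printed list | Items | Items naming seizures or seizure threshold |
|---|---|---|
| Exclusion criterion 17b, Chantix (Time Point 1) | 3 | 0 |
| Screening verbal review (Time Point 1) | 4 + 8 + 3 + 2 = 17 | 0 |
| Baseline re-confirmation (Time Point 3) | 4 + 8 + 3 + 2 = 17 | 0 |

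The four terms in each sum are NRT absolute contraindications (4), relative contraindications under the heading for non-NRT products (8), Chantix absolute (3) and Chantix relative (2). Restricted to the items headed Chantix, the count is 0 of 3 + 2 = 5 at each step. This is the fairer denominator.

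**Where seizures appear.** The word, singular or plural, occurs once in the gum and lozenge adverse-effect list and five times in the Chantix seizure warning: 1 + 5 = 6. All six are in Section 8a.

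**Could another item cover it?** The only candidate is underlying neuropsychiatric disease. It is not defined. Section 8a gives neuropsychiatric events (mood, psychosis, suicidality and similar) and seizures separate warnings. The item might be read to include epilepsy, but it does not clearly reach other factors that lower the threshold.

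**Is text missing from the list?** A figure is not shown inside the screening list as supplied. The baseline list prints the same two Chantix relative items with no gap between them, so the missing figure does not change the count.

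**Comparison with the other warnings.** Section 8a gives nine Chantix warnings: neuropsychiatric, seizures, alcohol, accidental injury, cardiovascular, somnambulism, angioedema and hypersensitivity, skin, and nausea. Two of them name a pre-existing condition as a risk: seizures and cardiovascular disease. The printed lists contain four cardiovascular prompts (recent infarction, arrhythmias, angina, uncontrolled high blood pressure) and no seizure prompt. This comparison is only supportive, because the cardiovascular prompts sit under the non-NRT heading and not under a Chantix heading.

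**The case against.** The strongest reply is that nothing here is contradictory. Section 8a asks for caution; it does not call a seizure history a contraindication, and a precaution may properly be left to the prescriber. Chantix is selected through Supplementary Document 2, a questionnaire used in a specialist tobacco clinic, which may already ask about seizures. Several further steps precede the first dose: review of the answers by the principal investigator, a call about Chantix, a consent discussion with a physician or mid-level provider, and a drug handout. The printed list is described as a focus, the baseline step covers any potential contraindication, and the screening note also covers concerns more broadly. Staff are not confined to the bullets.

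Much of this stands. It cannot be said that seizure history is never asked at screening, and no participant is shown to have been missed. Harm would need a Chantix prescription, a relevant history, a miss at every screening step, and then non-disclosure at baseline.

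It does not close the gap. The clinician steps named come before the baseline check and cannot stand in for it. The protocol does not say that the questionnaire is repeated at baseline; it says the contraindication review is repeated, and prints the list. Freedom to go beyond a list is not a prompt. The side-effect education at baseline and the 72-hour messages to Chantix users may bring out a history, but they are education and monitoring, not a question about the past. From Time Point 5 those messages also stop for users who have reported no adverse effects.

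It is also fair to say that a question about threshold-lowering factors is hard for a lay participant to answer. That bears on how the prompt is worded, not on whether it is needed.

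**Conclusion.** The concern holds. The protocol flags a seizure history or lowered seizure threshold as a reason for caution with Chantix, yet none of the 17 items printed at screening or at baseline, and none of the 5 headed Chantix, prompts for it. The consequence is clearest at baseline, which the protocol makes the confirmation before dosing.

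The conclusion rests on two assumptions: that the printed baseline list is what staff will work from, and that underlying neuropsychiatric disease is not a clear seizure prompt. If Supplementary Document 2 asks about seizures, the gap narrows to the repeat check but does not disappear.

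The protocol gives neither the number of participants who will receive Chantix nor the number with a seizure history, so no count of those affected is offered. This is an inexpensive patient-safety improvement that should be made. It does not affect the endpoint, sample size or analysis.

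**What to change.** Add one item to the Chantix relative contraindications at Time Point 1 and Time Point 3: a history of seizures, or other factors lowering the seizure threshold, in line with Section 8a. For the spoken review, use a plain question, such as whether the participant has ever had a seizure or been told they are at risk of one. Leave the detail of threshold-lowering factors to the clinician.

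Confirm that Supplementary Document 2 asks the same question, and add it if not.

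A positive answer follows the notes already in place: to the principal investigator at screening, and to the advanced practice provider at baseline. The choice between Chantix with caution and the patch stays with the clinicians. Because Section 8a calls for caution, the item should not become an exclusion criterion.

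The cost is one line in each of two existing verbal reviews, a check of one questionnaire, and probably a few more referrals for clinician review.

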The in-person baseline visit will include education about potential common and rare side effects of the prescribed medication. This is based on drug information that will be available to the patient in the enclosed package sent to the patient with nicotine pharmacotherapies (see “Supplementary Document 4”). **See Drugs/Substances/Devices and Risks sections in this protocol for more information on side effects.**

Participants will be provided a 24-hour contact phone number to discuss concerns about side effects with our study team for the duration of the 4-week study. The study team will refer these concerns within 24 hours to the PI or study coordinator. They will assist in providing recommendations regarding the continued administration, replacement or discontinuation of the medication). Participants will receive a text and/or voice response to the identified concern within 1 day of receipt. Participants may be advised to stop therapies. If both controller and rescue medications are stopped, the patient will be disenrolled from the study. If disenrolled, they will be provided contact information of local smoking cessation resources ([name] or tobacco treatment clinic at Bayview).

NOTE: All adverse effects or concerns about pharmacotherapy will be documented. The time, date, description of issue and response will be included in the documentation. All concerns will be documented within CRMS.

3RD STEP – CESSATION-DIRECTED MOTIVATIONAL INTERVIEWING

Brief motivational interviewing (MI) will also be delivered by the on-site research staff. The MI principles are derived from principles from the MDQuit.org program (see mdquit.org/cessation-programs/brief-interventions).

We will assist by enhancing motivation, ability and confidence through the following methods:

- Offer personalized, relevant feedback about the importance of quitting

Date: 01/10/2024

Principal Investigator: [name]

Application Number: IRB00224186

- Explore the individuals' perceived pros and cons of smoking and quitting
- Discuss the 4 R's of quitting tobacco use
 - i. Relevance: Help the individual identify why quitting tobacco is relevant to him/her.
 - ii. Risk: Encourage the individual to verbalize possible negative outcomes of tobacco use.
 - iii. Rewards: Help the individual identify the possible benefits of quitting tobacco use.
 - iv. Roadblocks: Help the individual to identify possible obstacles to quitting, including those from his/her past quit attempts.

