4TH STEP – DRUG AND STUDY VISIT REMINDERS

Participants will also be reminded that at all future study visits will occur remotely.

Participants will also be asked if they prefer to have the remaining study visits occur remotely by phone or video conferencing by Zoom. Participants will be notified that they will receive at least weekly text-messaging reminders providing updates regarding prescribed pharmacotherapies and study visit reminder dates/times.

They will be made aware that they will be contacted by text message (preferred) or phone on a scheduled basis as each week progresses. Messages will be of 2 types:

- Type 1: Reminder of the two offered dates & times of the following week's study visit video conference or phone call. The participant will choose one of the two dates for the study visit. Reminders will be sent 72 hours and 24 hours prior to each event.
- Type 2: For those prescribed Chantix®, follow-up will occur every 72 hours. The text or phone messages will ask if experiencing any medical issues on therapy [See Drugs/Substances/Devices and Risks sections in this protocol for more information on adverse effects]. The voice or text messages will state the question, “Are you experiencing any side effects or are you having any problems with taking Chantix?” If they text back “Yes”, the participant will receive a phone call by our research staff. The concerns will be reviewed with our medical specialist. The medical specialists may call the participant for further details and/or relaying the treatment plan. Concerns about the clinical status may warrant referral to the JHH Emergency Room or the Tobacco Treatment Clinic at Bayview Medical Center if acute medical care concerns arise.
 - If the medical recommendation is to discontinue BOTH the “acute” and “controller” pharmacotherapy, the patient will be disenrolled from the study. Participants who are disenrolled will be contacted by phone at the end of the intervention to employ the survey used at the final time point (See “Supplementary Document 6”). They will be provided contact information of local smoking cessation resources, including the state quitline ([name]) and Tobacco Treatment Clinic at Bayview Medical Center.
 - ❖ NOTE: We do not anticipate the discontinuation of both the “acute” and “controller” therapies based on our initial smoking cessation pilot at Douglass

Date: 01/10/2024

Principal Investigator: [name]

Application Number: IRB00224186

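### Section 8b defines adverse events for both NRT and Chantix but requires the written narrative only for NRT-reported events

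*Combined protocol and SAP*

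**What the plan says.** Section 8b, under the heading on reporting adverse events, defines a medication adverse event as "any symptom, sign, or experience that develops during the course of administering NRT (gum, lozenges or patches) or non-nicotine pharmacotherapies", with Chantix named as the non-nicotine drug. The next sentence sets the reporting duty: "The following report will be supplied as a narrative for all NRT-reported adverse events". Seven fields follow. One is "Whether alternative NRT or non-nicotine pharmacotherapy was prescribed"; the last is "Investigator assessment of the association between the event and study intervention".

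Other sections bear on the same events:

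- Section 4, Time Point 3, second step requires documentation of every adverse effect or concern about pharmacotherapy: "The time, date, description of issue and response will be included in the documentation". It adds "All concerns will be documented within CRMS". Time Point 4, second step repeats the four items.
- Section 4, Time Point 3, fourth step says that for Chantix users "follow-up will occur every 72 hours". Time Point 4 repeats this. From Time Point 5 the checks stop for users who have reported no adverse effect.
- Sections 6 and 8b have the PI review all concerns within 24 hours. Section 8b also has every adverse event followed until it resolves, stabilizes or is judged not to be caused by the study.
- Section 4, Time Points 1 and 2 give every participant an as-needed NRT gum or lozenge plus a controller, either the NRT patch or Chantix.

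**The concern.** Two adjacent sentences in Section 8b have different scopes: the definition takes in Chantix and the narrative requirement does not name it. *NRT-reported* is not defined, and it can be read by drug or by timing. The ambiguity affects Chantix users only, since patch users take nothing but NRT.

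At stake is a written record of how a Chantix event stands and whether the investigator associates it with the intervention. Section 8a attaches its extended warnings (neuropsychiatric, seizure, cardiovascular, angioedema, serious skin reactions) to Chantix, and only Chantix users get the 72-hour checks. The drug watched most closely is therefore the one the narrative sentence leaves out. Side-effect monitoring is also part of feasibility objective (c) in Section 2, so a consistent record serves the pilot's own purpose.

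**Working it through.** The plan gives no figure to reproduce; the check is mainly a comparison of texts.

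**1. What the term can mean.**

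- *By drug.* Only events put down to NRT need a narrative. Staff must then attribute the event before knowing whether a narrative is due, although association is itself a narrative field. Symptoms do not separate the drugs: nausea, abnormal dreams, constipation, flatulence and vomiting are the commonest Chantix reactions in Section 8a, and the same five head its gum/lozenge list.
- *By timing.* Any event during NRT use needs a narrative. Because Chantix users also receive gum or lozenge, some or many of their events are then covered. But the gum or lozenge is as-needed, so an event in a Chantix user who is not taking it could fall outside.

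**2. What is lost on the literal reading.** The seven narrative fields (Section 8b) against the four items documented for every drug (Section 4, Time Points 3 and 4: time, date, description, response):

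| Narrative field | Counterpart for all drugs |
|---|---|
| Study identifier | Implied by the participant's CRMS record |
| Description | Matched |
| Onset date | Partly (date) |
| Current status | None required in writing |
| Drug stopped | Partly (response) |
| Alternative prescribed | Partly (response) |
| Association with intervention | None required in writing |

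Tally: 1 matched + 1 implied + 3 partly covered + 2 without counterpart = 7. The follow-up rule in Section 8b needs someone to judge status, and sometimes cause, but does not say that the judgement is recorded.

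**3. How many participants.** The documents do not give the share on Chantix, so only a bound is possible, shown here for nausea alone.

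- Inputs: 48 participants expected to continue (Section 4, Time Point 1, Note 1 on enrollment); nausea in up to 30% on Chantix (Section 8a); Chantix share *s*, assumed.
- Formula: upper limit = 48 × *s* × 0.30.
- *s* = 0.25: 3.6. *s* = 0.50: 7.2. *s* = 0.75: 10.8. *s* = 1.00: 14.4.
- Lower limit: 0, if nobody takes Chantix or all such events already count as NRT-reported.

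With the enrollment cap of 60 in place of 48, the top of the range is 60 × 1.00 × 0.30 = 18.

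**The case against.** The strongest reply is that context settles the meaning. The sentence sits under a general adverse-event heading, directly after a definition naming both drug classes; its fields are generic, and one mentions non-nicotine therapy. Section 8b goes on to speak of all adverse events and gives a switch from Chantix to patch as its example. Nothing suggests that the team meant to exempt Chantix. This stands as evidence of intent, and is why the wording is probably a slip. It does not change what the sentence requires.

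A second reply is that existing coverage is fuller than the tally allows. Time Point 3, second step has the team give "recommendations regarding the continued administration, replacement or discontinuation of the medication", and the response must be documented. A switch would also normally leave a prescription record in Epic. That is fair for the stopped-drug and alternative-prescribed fields, which could be counted as covered. The two fields with no counterpart remain.

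Third, Section 8c has the PI review all unanticipated problems and sends major deviations to the IRB at once. This is a further route for harmful events, but it sets no narrative content. The supplementary forms, which are not in the documents, may carry the missing fields; the conflict within Section 8b would remain.

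Finally, the nausea range rests on an extreme assumption about Chantix use and counts participants with one symptom, not narratives. That is correct: it is a bound, not a forecast, and the point does not depend on it.

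**Conclusion.** The concern holds, as a minor inconsistency in safety reporting. The narrative requirement is narrower than the definition it follows. On the literal reading, two of seven fields, current status and association, have no required written counterpart for Chantix events in the documents provided.

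Detection, PI review and follow-up are intact. No outcome in Section 7 uses these fields, so design and analysis are unaffected. The nausea bound of 0 to about 14 of 48 assumes, at its top, universal Chantix use, the 30% ceiling and no event already covered. Confidence is high that the wording is inconsistent and only moderate that a narrative would be missed in practice.

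**What to change.** In Section 8b, change the scope of the narrative from *NRT-reported* events to *all adverse events reported on any study drug (NRT or Chantix)*. This matches the section's own definition and removes both readings, so staff need not attribute an event before deciding whether to write it up.

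The cost is one phrase and some additional narratives. Their number cannot be fixed from the documents; for nausea alone the bound above applies, and it falls to the extent that events in Chantix users are already treated as NRT-reported.
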